- Other concomitant laparoscopic or prolapse and anti-incontinence procedures (e.g., laparoscopic supracervical hysterectomy, cystocele repair, rectocele repair or mid-urethral sling procedures) will be performed at the primary surgeon's discretion.

Exclusion Criteria:

- Inability to comprehend written and/or spoken English
- Inability to provide informed consent
- Medical illness precluding laparoscopy
- Need for concomitant surgeries not related to pelvic organ prolapse or incontinence
- Sacrocolpopoperineopexy
- Need for dual flat mesh for sacrocolpopexy procedure (determined by surgeon)

Study Procedures:

Study Identification and Recruitment

Potential subjects will be identified by members of the Center for Urogynecology & Pelvic Reconstructive Surgery at the Cleveland Clinic Main campus and Fairview Hospital. Eligible patients that agree to participate will be provided written informed consent administered by the collaborators listed on this IRB.

Randomization

All subjects will be predetermined by their surgeon to undergo either a laparoscopic or robotic assisted laparoscopic sacrocolpopexy depending upon their clinical evaluation. The participants will then be randomized to either Restorelle® or Vertessa® Y sacrocolpopexy according to a computer-generated randomization schedule with random block sizes with the use of the SAS statistical software package (SAS Institute, Cary, NC). All patients will be blinded to their assignment.

Office Interventions

All patients will be seen for a preoperative visit and then postoperatively at 6, 12 and 24 months. At each visit, a vaginal exam and a complete Pelvic Organ Prolapse Quantification (POP-Q) exam will be performed. Patients will also be asked to update their medical history. In addition, patients will be asked to complete the Pelvic Floor

Distress Inventory (PFDI-20), Incontinence Severity Index (ISI) and Pelvic Organ Prolapse/Urinary Incontinence Sexual Questionnaire (PISQ-12) questionnaires at the pre-operative visit as well as the 6, 12, and 24 month postoperative visits. Completion of these questionnaire is the only additional assessment that is specific to participation in this study and is not usually included as part of the standard care of sacrocolpopexy. It should take no more than 10-15 minutes to complete the questionnaires. The study subjects will not be exposed to any additional risk by participating in this study except for the inconvenience of completing the questionnaire.

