Data Collection & Management:

Preoperative data will include the following:

- Patient age, race, vaginal parity, menopausal state, BMI, prior prolapse surgery, preoperative prolapse stage
- PFDI-20, ISI, PISQ-12
- Preoperative hemoglobin

Data points recorded during the procedure will include:

- Total OR time = operating room time of entry and exit
- Total Case time = time from incision to closure
- Concomitant procedures
 - Supracervical hysterectomy
 - Anterior colporrhaphy
 - Posterior colporrhaphy
 - Perineorrhaphy
 - Midurethral sling
- Estimated blood loss
- Intraoperative complications
 - EBL > 500cc
 - Vascular Injury
 - Cystotomy
 - Ureteral Injury
 - Bowel Injury - small bowel, large bowel, rectal

Postoperative data will include the following: 6, 12, 24 months

- POP-Q exam (performed by a provider blinded to the mesh used at the time of the procedure)
- PFDI-20, ISI, PISQ-12

- Review of electronic medical record (inpatient notes, d/c summary, ER visits), assessing for postoperative complications
 - Reoperation for immediate complications = reoperation within 30 days of surgery
 - Abdominal Wound infection = fascial, subcutaneous, cutaneous infection requiring antibiotic treatment
 - Hematoma = intrapelvic/abdominal
 - Vaginal cuff cellulitis/Pelvic Abscess = requiring IV/PO antibiotic therapy and/or transvaginal, transgluteal or percutaneous drainage
 - DVT/PE = diagnosed with Doppler US or CT scan
 - Reoperation for SUI with pubovaginal sling (synthetic or fascial), colposuspension, injection with periurethral bulking agents
 - Reoperation for mesh exposure
 - Reoperation for recurrent POP
 - Bowel Injury/Bowel Obstruction = enterotomy, perforation, ileus, partial/complete obstruction
 - Port site or incisional hernia
 - Need for any radiologic imaging
 - Lower urinary tract injury = bladder, ureteral
 - Neurologic Injury = brachial plexus, abdominal wall (ilioinguinal, iliohypogastric), lower extremity (femoral, sciatic, common peroneal)
 - Pulmonary complications = pneumonia, pulmonary hypertension, pulmonary edema within 14 days of surgery
 - Cardiac = ACS, MI, HF within 14 days of surgery
 - Postoperative ICU admission

[figure not shown]

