There will be 2 arms to this study: laparoscopic (robotic-assisted and conventional) sacrocolpopexy with Restorelle® Y mesh and laparoscopic (robotic-assisted and conventional) sacrocolpopexy with Vertessa® Y mesh. Subjects will be chosen based on surgeon preference to either undergo RA LSC ASC or conventional LSC ASC. They will then be randomized to either the Restorelle® or Vertessa® Y mesh arm. We determined that if there is no difference between the two Y mesh grafts, 90 patients are required to be 70% sure that the upper limit of a one-sided 95% confidence interval will exclude a difference in favor of the Restorelle® group of more than 10%. We will account for a potential 10% subject drop out and loss to follow-up as well as unforeseen factors in recruiting and will plan to recruit 50 subjects to each arm, for a total of 100 subjects.

All statistical analyses will be done using jmp 12. We will use descriptive statistics to show our demographic and baseline data: categorical variables will be presented as n/N (%) with 95% confidence intervals and continuous variables will be presented as mean +/-SD [range]. The two Y mesh grafts will be compared. Differences between the groups in the primary outcome of surgical success and other categorical outcomes were evaluated using generalized linear models. We will control for LSC ASC and RA LSC ASC by performing a logistic regression.

Summary of tasks for study:

	Preop	6 mo	12 mo	24 mo
Informed consent	X			
Demographic data	X			
Randomization	X			
PFDI-20	X	X	X	X
ISI	X	X	X	X
PISQ-12	X	X	X	X
POP-Q	X	X	X	X
Review of d/c summary, chart, postop Hct, complications (ER visits, etc)		X		
Update medical history		X	X	X

References:

3. Porges RF & Smilen SW. Long term analysis of the surgical management of pelvic floor support defect. *Am J Obstet Gynecol* 1994;171:1518–1528.
4. Birch C. The use of prosthetics in pelvic reconstructive surgery. *Best Pract Res Clin Obstet Gyn* 2005;19(6):979-991.
5. Chu CC & Welch L. Characterisation of morphological and mechanical properties of surgical mesh fabrics. *J Biomed Res* 1985;19:903–916.
6. Kaupp HA, Matulewicz TJ & Lattimer GL. Graft infection or graft reaction? *Arch Surg* 1979;114:1419-1423.

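### The primary comparison adjusts for surgical route but not for the preoperative prolapse stage already recorded; adding stage is a cheap improvement, mainly in protection against an unlucky split

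*Combined protocol and SAP*

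**What the plan says.** All references are to the combined protocol and SAP.

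- **Analysis Plan, method.** "Differences between the groups in the primary outcome of surgical success and other categorical outcomes were evaluated using generalized linear models". That sentence lists no covariates. The next one names the only factor to be adjusted for: "We will control for LSC ASC and RA LSC ASC by performing a logistic regression". The plan does not say which of the two models decides non-inferiority.
- **Analysis Plan, decision rule.** The size is justified by "90 patients are required to be 70% sure that the upper limit of a one-sided 95% confidence interval", which is to "exclude a difference in favor of the Restorelle® group of more than 10" percent, on the premise "if there is no difference between the two Y mesh grafts".
- **Data Collection & Management, preoperative data.** The list reads "Patient age, race, vaginal parity, menopausal state, BMI, prior prolapse surgery, preoperative prolapse stage". The Analysis Plan gives baseline data a descriptive role only.
- **Study Procedures, Randomization.** Allocation follows a "computer-generated randomization schedule with random block sizes". No stratum is named.
- **Primary Outcome.** The composite counts apical descent, wall descent past the hymen, bulge symptoms and retreatment for prolapse.

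**The concern.** The plan already accepts covariate adjustment, but spends it on route, which the surgeon chooses, and leaves out the baseline measurement of what the outcome itself counts. Stage is therefore handled in neither the design nor the analysis. With 90 evaluable women, few failures and a verdict that turns on one confidence limit, a visible difference in stage between arms could tip the result. An equal mesh that drew more advanced prolapse would find it harder to pass, and a worse mesh that drew less would find it easier. Stage will appear in the baseline table. If the arms look unequal there, an adjustment chosen afterwards will carry little weight.

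**Working it through.** **1. The plan's own figure.** Evaluable women per arm = (1.645 + 0.524)² × 2p(1 − p) / 0.10². The plan states no p. At 95% success this is 44.7, so 45 per arm and 90 in total, and 90 / 0.9 = 100 recruited. The 95% is back-solved. At 89%, the anatomic success rate cited in the Background, the formula gives 93 per arm, and power at 45 per arm is 45%. Both failure levels, 5% and 11%, are carried below.

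**2. Assumptions not in the documents.** Half the women are advanced stage and 30% are robotic. Failure by stage (not advanced v advanced) is 2% v 8% (mean 5%), 6% v 16% (mean 11%) or 3% v 19% (mean 11%). These are strong effects, with odds ratios of about 4.3, 3.0 and 7.6. Weaker ones follow in step 6.

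**3. How often stage is unbalanced.** The SD of the difference in share advanced is √(2 × 0.5 × 0.5 / 45) = 0.105. Fifteen points is 6.75 women, so at least 7. The SD of the count difference is √(90 × 0.25) = 4.74. With a continuity correction, 6.5 / 4.74 = 1.37, a two-sided probability of about 17%, or about 8% in each direction.

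**4. Shift in the estimate** = imbalance × stage effect. At exactly 15 points it is 0.15 × 0.06 = 0.9, 0.15 × 0.10 = 1.5 and 0.15 × 0.16 = 2.4 points. Imbalances beyond the threshold average about 19 points, which gives 1.2, 1.9 and 3.0 points.

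**5. Power when the meshes are equal and Vertessa has the excess.** Route only: Φ((0.10 − shift)/SE − 1.645), with SE = √(2p(1 − p)/45), which is 0.0459 at 5% failure and 0.0660 at 11%. With stage: no shift, and SE × √(1 − R²), where R² = 0.25 × (stage effect)² / p(1 − p), p being the failure rate. R² is 1.9%, 2.6% and 6.5%, worth about 2 to 6 of 90 women. The simulation (20,000 trials per scenario) used identity-scale regression with HC2 errors.

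| Failure by stage | By formula: route only v with stage | Simulated: route only v with stage |
|---|---|---|
| 2% v 8% | 61% v 71% | 62% v 72% |
| 6% v 16% | 34% v 46% | 37% v 48% |
| 3% v 19% | 28% v 47% | 28% v 47% |

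About 1,700 trials fall in each conditional subset, so simulation error is roughly √(0.37 × 0.63 / 1,700) = 1.2 points. Repeated runs give 27% to 37% v 46% to 48% at 11% failure, and about 64% v 72% at 5%.

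**6. False non-inferiority when Vertessa is truly 10 points worse and Restorelle has the excess** (12,000 trials per scenario, harm a flat 10 points at every stage).

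| Failure by stage | Route only | With stage |
|---|---|---|
| 2% v 8% | 7.5% | 6.1% |
| 6% v 16% | 10.6% | 6.6% |
| 3% v 19% | 10.4% | 6.1% |
| 8% v 14% (odds ratio 1.9) | 7.0% | 5.4% |
| 4% v 6% (odds ratio 1.5) | 7.6% | 6.9% |

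If harm instead scales with baseline risk, the three strong-effect scenarios give about 10% to 13% with route only. Taken together, those three scenarios give about 8% to 13% with route only v 5% to 8% with stage.

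**7. Over all trials.** False-positive rates are about 5% to 7% with either model. Power rises by about 0 to 2 points. With equal meshes the two models reach opposite verdicts in 5% to 8% of trials.

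**The case against.** The strongest reply is that nothing here is an error. Under randomization the confidence interval already allows for chance imbalance in stage: an excess in one arm raises the false-positive rate, an excess in the other lowers it, and the average stays put. Any prognostic factor can be made to look dangerous by conditioning on an unlucky split, and prior prolapse surgery and BMI are recorded too. That stands, and it rules out a claim of bias or of an inflated overall error rate.

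It also stands that every stage effect above is assumed. A reader might infer that an imbalance doubles the stated 5% error. That needs a strong stage effect and, for the higher figures, harm that scales with baseline risk. With a flat 10-point harm the rate is about 8% to 11%, and with a weak or moderate stage effect about 8%. A reader might also take the shift to be as large as 4 points; on these assumptions it is about 1 to 3 on average.

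Nor is another parameter free with so few events: 90 × 0.05 = 4.5 and 90 × 0.11 = 9.9 failures are expected. In simulation, however, overall error rose by no more than about 0.4 point. What the objection does not answer is the choice of covariate. The plan already adjusts for one factor, and stage is the recorded variable closest to the outcome.

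**Conclusion.** The point holds as a cheap improvement, not as a flaw that invalidates the test. Route is the only covariate named, stage is already collected, and no stratification by it is stated. The benefit is conditional. It needs stage to predict failure and the arms to differ by about 15 points or more, which happens in roughly one trial in six if half the women are advanced. In that case, with a strong stage effect and the excess in Vertessa, an equal mesh loses about 8 to 20 points of power. With the excess in Restorelle, false non-inferiority is modestly above nominal. With a weak stage effect the gain is close to nil. The documents do not support reading the omission as letting imbalance pass unchecked into the decision, because the interval already carries that uncertainty. The unstated success rate behind the 90 women weighs more on the non-inferiority conclusion than this does.

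**What to change.** In the Analysis Plan, pre-specify preoperative prolapse stage as one two-level covariate beside route in the primary model, with the cut fixed before allocation is opened. Take the mesh difference in failure risk and its one-sided 95% upper limit from that same model, either by standardization or by identity-scale regression with robust standard errors, so that the result is on the scale of the 10-point margin. A logistic coefficient alone is not on that scale. Report the route-only result as a sensitivity analysis.

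The cost is one sentence, with no extra data and no extra women. The small downside is one more parameter with about 5 to 10 expected failures. For that reason stage should stay at two levels and no further covariates should be added.
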